9.7.4 Sequence of Analyses

The study analysis and results (statistical tables only) conducted using the Danish data are planned to be delivered as interim analysis. The Danish data is expected to be received and analyzed prior to the Swedish data. Therefore, in order to deliver the study results to the Sponsor as soon as result for Denmark is available, the interim analysis with Danish data only was planned. However, the data application processing time for Denmark has increased significantly due to Coronavirus Disease 2019 (COVID-19). With the estimate made available by end of 2020, the data application period will be similar for Sweden and Denmark. In this case, there might not be a need for an interim report. PPD is conducting an ongoing monitoring of update from Danish authorities regarding this update.

9.8 Quality Control

The study protocol has been written by following the European Network of Centres for Pharmacoepidemiology and Pharmacovigilance (ENCePP) Code of Conduct (42) and the Guideline for Good Pharmacoepidemiology Practices (GPP) by the International Society for pharmacoepidemiology (43). The study protocol and as well as results will be published in the EU electronic register of post-authorization studies (EU PAS register) maintained by the EMA.

At the study level, all aspects of the study from protocol development to the reporting of the results are conducted within the work-frame of PPD Quality Management System (QMS) and in accordance to the following policies and procedures:

- POL_QA_001 “Quality Management System” policy
- POL_QC_001 “Quality Control Strategy” policy
- SOP_QC_002 “Quality Control of Project Deliverables”

According to the policies and procedures above, a Quality Control plan for the study will be developed and executed, which will include quality control on study methodology, statistical analysis plan, programming, data management and analysis, and study report including study results and conclusions. Furthermore:

- The study Quality Control plan will establish ownership for the execution of the individual Quality Control steps. The principle of the independence of Quality Control applies.
- PPD project management will ensure that individuals responsible for the execution of specific Quality Control steps will have knowledge, capability and experience which are adequate for the task.
- The result of the execution of the individual steps of the Quality Control plan will be documented, and include the required corrective actions, if any.
- The execution of any required corrective action will be documented.

- The executed Quality Control plan will be subjected to a final review and approval for sufficiency and completeness by the PPD project management team.
- The project management will also ensure that PPD employees assigned to the project are trained on protocol and project-specific procedures, as per PPD procedure RWI_WI_PM0035 “Real-World Project Specific Training and Staff Transition”.

The study will be conducted as specified in this protocol. All revisions to the protocol must be approved by the principal investigator and the Sponsor. All changes to the protocol shall be properly documented as protocol amendments and when necessary such protocol amendments are delivered to source data register holders.

Quality control will also be performed on the retrieved register data, including controlling the inclusion of compulsory variables, such as study identification number (SID), hospitalization, and the main diagnosis, in the delivered register data. If data are missing or incorrect, the dataset is sent back to the register holder for correction.

All programs for data management and data analyses will be written by the study statistician(s). A quality control check of these programs will be carried out by a statistician other than the one who writes the program. All processes from data management leading to dissemination of study results will undergo quality control checks for programs, result tables, and written text. A detailed audit trail of all documents (programs, result tables, reports) along with quality control processes will be maintained.

9.9 Limitations of the Research Methods

9.9.1 Selection Bias

Owing to the use of secondary data originally collected for purposes unrelated to this study, biased results arising from how women are selected into the study is considered a minor issue. Selection will not depend on both exposure status and risk factors for the outcomes, which can otherwise lead to biased exposure-outcome associations. Moreover, all registers used in the study have nationwide coverage and employ mandatory reporting for publicly- and privately-operated units. The Swedish IVF register is an exception as being a quality register, to which reporting is not mandatory; however, close to 100% of all IVF clinics in Sweden report data to the register (33).

In Denmark, a small volume of sales of the study drugs were made to hospitals during the period 2010-2019, which means that some cycles may not be included in the analysis. However, since the percentage of in-hospital sales constituted less than 2.5% and less than 1% of total sales for HP-hMG and follitropin alfa (*i.e.*, rhFSH-alfa reference product and rhFSH-alfa biosimilar products combined), respectively, it is expected to have a minimal impact on the study (44).

In the Nordics, the validity and completeness of the medical birth registers for use in epidemiological research is considered to be high (45), and it is expected that obtaining information on the primary outcome, live birth, will be nearly 100% complete. In the SMBR, for example, it is estimated that 97-99% of all newborn babies in Sweden are reported to the register, and the number of children reported to the SMBR are validated against population registration data (46). Further, the Q-IVF contains over 240,000 registered treatments to date from all public and private IVF-treating clinics in Sweden and is considered one of the most complete, national IVF registers in the world. In the recently published 2020 Q-IVF Annual Report, which reported data from year 2018, there were only 13 cases of initiated fresh IVF cycles with missing data on treatment or pregnancy outcomes; accordingly, the proportion of treatments lost to follow up amounted to only 0.14% of the total 11,061 annual fresh IVF cycles (33). In 2017, a similarly very low proportion (0.13%) lost to follow up was reported in the 2019 Q-IVF Annual Report (47). Researchers suggest that loss of follow up in these few cases may be because patients came from/have moved abroad. However, as more than 99% of all initiated IVF treatments contain sufficient follow up to assess study outcomes, the few cases lost to follow up is expected to have a minimal impact in the study. The Q-IVF has been used widely in research previously (41,48–51).

Similar to Sweden, in Denmark, the DMBR has a high completeness, particularly for the primary outcome of live birth, since all newborn children are registered in the DMBR (52–54). In the early period when the DIVF was first established (1994-2005) and included only paper-based reports,

the Danish National Board of Health suspected that were to some degree an under ascertainment of the true number of treatments initiated due to incomplete capture, noting that the use of electronic capture in future updates would improve quality (55,56). However, as only electronic reports are included during the period under study (2010-2020), previously identified limitations related to underreporting would not be an issue in this study. All treatment cycles and measurements on pregnancies from private and public IVF clinics are required to be reported, and the DIVF during the study period is based on electronic capture and complete and validated data (52). Similar to the Q-IVF, the DIVF has been used extensively in research (27,40,54,57,58).

As in any study assessing cumulative live birth rates of IVF treatment, uncertainty remains around end outcomes in those who discontinued treatment, had they continued. This uncertainty will be addressed by the estimation of conservative estimates and, in a sensitivity analysis, optimal estimates for the primary objective MC-CLBR outcome, based on different assumptions of live birth rates in women who discontinued treatment (see Analysis 2 in Table 8). Similarly, the impact on the conservative and optimal MC-CLBR estimates of extending the minimum follow-up to 2 years will also be explored (see Analysis 3 in Table 8).

Further, prescribing patterns of the study drugs are likely to vary to some extent across the study period. If one drug was favored over the other in the early part of the study period, the probability of observing all live births in up to five stimulation cycles using that drug would be higher than for the other one (due to availability of data with longer follow-up). Based on the feasibility assessment of the use of the study drugs in Denmark and Sweden, it is known that the use of rhFSH-alfa biosimilar products has increased gradually, with a relatively larger proportion observed during the latter part of the study period, compared with rhFSH-alfa reference product (37). Hence, it cannot be ruled out that this may lead to a downward bias for the cumulative live birth rate outcomes following COS with rhFSH-alfa biosimilar products.

Prior to October 2016, induced abortions were not recorded in the SNPR, meaning ascertainment of this component of pregnancy loss will rely solely on the Q-IVF prior to this date. Furthermore, abortion statistics based on anonymized data show that ~70% of all induced abortions between 2018 and the second quarter of 2020 were medical abortions completed at home (59). This suggests the data on induced abortions captured in the SNPR in 2016-2020 is likely incomplete.

9.9.3 Confounding by Baseline Characteristics

Confounding by baseline characteristics is a key challenge in non-interventional studies of drug treatment effects. Although the study drugs are equally recommended in IVF treatment guidelines and used interchangeably, differences in baseline characteristics, e.g., in terms of cause of infertility or previous IVF treatment, between the study cohorts cannot be ruled out. To minimize the potential for confounding, IPTW methods accounting for a broad range of characteristics, including history of IVF treatment, fertility-related health characteristics, and other factors potentially associated with the study outcomes will be applied.

9.9.4 Unmeasured Confounding

Although a broad range of characteristics will be collected for this study, some relevant predictors of treatment outcomes, such as the antral follicle count and anti-Müllerian hormone levels (60,61),

will not be available from the data collected in Sweden and likely only available for a subset of the Danish study population. Unmeasured confounding cannot be ruled out. However, a sensitivity analysis performed for Denmark will explore the effect of controlling for anti-Müllerian hormone levels and other relevant outcome predictors available from the RLRR (see Analysis 4 in Table 8).

9.9.5 Study Size and Time Trends

The study size depends on the inclusion period and the incidence of fertility treatments in both countries of study. Differences in standard of care, treatment patterns and success rates are expected to some extent over time. Legal regulations on eligibility for IVF treatment (e.g., donor gametes, lesbian couples, single women) and rules for storage of frozen oocytes and embryos have also changed during the study period. However, with an overall study period spanning 11 years from 2010-2020, any changes in standard of care are expected to have limited impact on the consistency of results across the study period.

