9.3.2 Other Variables (Covariates)

In addition to the outcome and exposure variables outlined in Section 9.1.2 and Section 9.3.1, the covariates of interest in this study are listed below and classified according to their intended use in the analysis (Table 1).

The variables are generally described as measured in relation to each IVF/ICSI stimulation cycle; however, variables used to derive the outcome variables may also apply to any linked FET cycles, depending on the outcome under study. Variables indicated as being candidates for regression modeling are determined after the decision on which gonadotropin to use for COS has been made. These variables will therefore not be included in the PS but may instead be added as independent covariates in the IPTW-weighted regression model (see Section 9.7.3.1 for further details).

For variables identified in the registers by ATC, ICD-10 and/or procedure codes, these operational definitions are provided in Appendix 3 (Section 14.3.3).

Table 1. List of covariates and their use in the study

Variable	Measurement scale	Baseline characteristic	Candidate variable for PS	Candidate variable for additional adjustment
Demographic characteristics				
Age at stimulation cycle index date	Continuous	X	X	
IVF/ICSI treatment characteristics				
Treatment type (ICSI, IVF, ICSI + IVF; FET)	Categorical	X	X	
Type of clinic (private, public)	Categorical	X	X	
Calendar year of stimulation cycle	Continuous	X		
GnRH protocol (agonist, antagonist)	Categorical	X	X	
Cycle cancellation (timing within cycle)	Categorical	N/A (used to derive outcome variable)		
Date of cycle cancellation	Continuous	N/A (used to derive outcome variable)		
Type of drug for ovulation triggering	Categorical	X		X

Variable	Measurement scale	Baseline characteristic	Candidate variable for PS	Candidate variable for additional adjustment
Type of drug for luteal phase support	Categorical	X		X
Date of follicular aspiration	Continuous	N/A (used to derive outcome variable)		
Date of embryo transfer	Continuous	N/A (used to derive outcome variable)		
Number of days of embryo cultivation ⁺	Numerical	X		X
Date of embryo cryopreservation	Continuous	N/A (used to derive outcome variable)		
Embryo cryopreservation method (slow freezing, vitrification)	Categorical	X		X
Date of embryo thawing	Continuous	N/A (used to derive outcome variable)		
Number of embryos thawed	Continuous	N/A (used to derive outcome variable)		

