Date of pregnancy test	Continuous	N/A (used to derive outcome variable)		
Pregnancy test result or indicator for pregnancy	Continuous	N/A (used to derive outcome variable)		
Date of ultrasound	Continuous	N/A (used to derive outcome variable)		
Date of pregnancy loss	Continuous	N/A (used to derive outcome variable)		
Other clinical characteristics				
Height/weight or BMI	Continuous	X	X	
Obesity	Categorical	X	X	
Bariatric surgery	Categorical	X	X	
Smoking status*	Numerical	X	X	

Variable	Measurement scale	Baseline characteristic	Candidate variable for PS	Candidate variable for additional adjustment
Type 1 diabetes mellitus	Categorical	X	X	
Type 2 diabetes mellitus	Categorical	X	X	
Antidiabetic drugs	Categorical	X	X	
History of thromboembolic events	Categorical	X	X	
Use of thrombosis prophylaxis	Categorical	X	X	
Porphyria and other relevant conditions [#]	Categorical	X	X	
History of any cancer	Categorical	X	X	
Medical history, fertility-related				
Number of previous failed COS	Categorical	X	X	
History of failed IUI	Categorical	X	X	
History of COS with a study drug	Categorical	X	X	
History of COS with a non-study drug	Categorical	X	X	
Previous delivery with at least one live birth following IVF	Categorical	X	X	
Parity	Categorical	X	X	
OHSS	Categorical	X	X	
Amenorrhea or oligomenorrhea	Categorical	X	X	
PCOS	Categorical	X	X	
Endometriosis	Categorical	X	X	

Variable	Measurement scale	Baseline characteristic	Candidate variable for PS	Candidate variable for additional adjustment
Female infertility diagnosis	Categorical	X	X	
Female factor infertility*	Categorical	X	X	
Male factor infertility*	Categorical	X	X	
Idiopathic factor infertility*	Categorical	X	X	
Medical history, laboratory test results (value at most recent record on or prior to stimulation cycle index date) [†]				
Anti-Müllerian hormone, pmol/L	Continuous	X	X	
FSH, IU/L	Continuous	X	X	
Thyrotropin, mIU/L	Continuous	X	X	
Prolactin, mIU/L	Continuous	X	X	

BMI: body mass index; COS: controlled ovarian stimulation; FET: frozen embryo transfer; FSH: follicle-stimulating hormone; GnRH: gonadotropin-releasing hormone; ICSI: intracytoplasmic sperm injection; IUI: intrauterine insemination; IVF: in vitro fertilization; IU: international unit; L: liter; mIU: milli-international unit; OHSS: ovarian hyperstimulation syndrome; PCOS: polycystic ovarian syndrome; pmol: picomole; PS: propensity score.

Notes:

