[†]Not available in Denmark and available from 2015 in Sweden; can be approximated by subtracting the date of follicular aspiration from the date of embryo transfer for stimulation cycles.

* Available for Denmark only (from the DIVF).

Full list of conditions to be considered is provided in Appendix 3 (Section 14.3.3).

[‡] Available for Denmark only [from the Danish Register of Laboratory Results for Research (RLRR); see Section 9.4.1]. Because completeness is uncertain, these data will be used in a sensitivity analysis only, as described in analysis 4 in Table 8.

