9.4.1 Denmark

The Civil Registration System (CPR) holds base information on personal identification number, date of birth, sex, immigration/emigration dates, ethnicity/country of origin, date of death, etc. since 1970.

The Danish In-vitro Fertilization Register (DIVE) was established to provide evidence for the Danish National Board of Health's monitoring of ART treatments in Denmark as well as providing data for research. The register contains information on ART treatments at both public and private fertility clinics in Denmark, including the cause of the infertility, fertilization method, origin of semen and oocytes, and vitrification methods. Pregnancy outcome is not recorded. The DIVE has been in operation since 1994, with later improvements in 2006. Starting from this year, information was added on, e.g., IUI, the woman's and partner's life style (weight, alcohol and smoking habits), results from ultrasound examination, including number of gestational sacs with/without heartbeat, choice of cryopreservation method, and whether transfer of one embryo only (fresh or frozen) was an elective or non-elective procedure. The register is updated monthly.

It is possible to submit changes to already reported information. With a lag of approximately 2 months, it is estimated to capture the majority of subsequent changes to already reported information.

The Danish National Patient Register (DNPR) contains information on the Danish population's encounters at hospitals (secondary care) (28,29). The register is a central tool for the health care authorities to monitor diseases and treatments, and the activities at the individual hospitals. Data on activities and diagnoses in primary care at general practitioners (GPs) and specialists in private practice is not included. The register contains information on date of admission and discharge, type and setting of care (inpatient or outpatient), diagnoses (classified according to the ICD-10 classification), examinations, surgical and non-surgical procedures, and Diagnosis Related Group (DRG) costs. Data is available from 1977 for inpatient somatic admissions. Since 1995, outpatient visits, emergency room visits and encounters at psychiatric wards are also included. DRG costs are available since 2002.

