9.7.3.1 Propensity Score Methodology

PS-based methods are frequently used in non-interventional studies to control for confounding when estimating treatment effects (38). In this study, the PS weighting will be implemented using IPTW approach.

PS, typically obtained using logistic regression models, are covariate summary scores that indicate the individual probability of having a treatment initiated with the study drug against the comparator drug, given the observed baseline characteristics. In PS weighting with IPTWs, each subject is weighted by the inverse probability of receiving the treatment they have actually received, *i.e.*, $1/PS$ in the study drug cohort and $1/(1-PS)$ in the comparator drug cohort (22). In other words, the PS weighting with IPTW creates a pseudo-population of study drug cohort and the comparator drug cohort that are weighted samples of the original study cohorts but have the same covariate distribution as the overall original study cohorts (22). Thus, using the IPTW-weighted study cohorts will remove confounding from all covariates included in the PS model, and give the estimate for the treatment effect in the overall population (22).

For this study, the IPTW approach will be based on pairwise PS estimation for i) rhFSH-alfa reference product cohort and HP-hMG cohort, and ii) rhFSH-alfa reference product cohort and rhFSH-alfa biosimilars cohort. The PS will be estimated for the stimulation cycle initiation with the study drug (rhFSH-alfa reference product) against the comparator drug (HP-hMG or rhFSH-alfa biosimilar product) by using logistic regression, including covariates as indicated in Table 1 (Section 9.3.2). Based on the estimated pairwise PS, i) IPTW-weighted rhFSH-alfa reference product cohort and IPTW-weighted HP-hMG cohort, as well as ii) IPTW-weighted rhFSH-alfa reference product cohort and IPTW-weighted rhFSH-alfa biosimilars cohort will be created.

Diagnostic measures will be used for assessing the success of the PS model to account for confounding. In addition, the distribution of IPTWs will be checked and in case very large weights are observed, the stabilized, trimmed and truncated weights will be considered to avoid increasing the variability of the treatment effect estimates due to very large weights (38).

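### Origin of semen is recorded in the Danish IVF register but has no role in Table 1, although eligibility for treatment changed during the study period

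*Protocol*

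**What the plan says.** - Protocol Section 9.9.5 names "Legal regulations on eligibility for IVF treatment (e.g., donor gametes, lesbian couples, single women" among the legal rules that changed within the study period. It gives no country, date, direction or size. Its closing sentence expects little effect from changes in standard of care and does not return to eligibility.
- Section 9.4.1 describes the content of the Danish IVF register (DIVF) as "including the cause of the infertility, fertilization method, origin of semen and oocytes, and vitrification methods". The description of the Swedish register (Q-IVF) in Section 9.4.2 does not mention semen origin.
- Section 9.3.2 states that, beyond outcomes and exposure, "the covariates of interest in this study are listed below and classified according to their intended use in the analysis (Table 1". Section 9.7.3.1 builds the PS by logistic regression "including covariates as indicated in Table 1 (Section 9.3.2".
- Table 1 has no row for semen origin, donor use or partner status. "Calendar year of stimulation cycle" is marked as a baseline characteristic only.
- The nearest PS candidates are age, type of clinic, parity, female infertility diagnosis, "History of failed IUI", and the female, male and idiopathic factor variables. "Male factor infertility" and the other two factor variables carry the note "Available for Denmark only (from the DIVF".
- Section 9.9.2 says that prescribing patterns probably varied over the period and that biosimilar use grew, with more of it in the later years.

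**The concern.** Section 9.9.5 concedes that the population eligible for IVF changed. Women treated because they have no male partner may differ in prognosis from couples treated for infertility. If their share rose or fell while product use also moved, or if it varied between clinics with different product preferences, semen origin would be a confounder of the live birth comparisons.

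The variable is fixed before treatment and sits in a register that is already being extracted for Denmark. Leaving it out of Table 1 means that the imbalance is neither corrected nor made visible. Bias of this kind does not shrink as the cohorts grow, and the cohorts here run to thousands of women.

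**Working it through.** **Step 1. Can semen origin enter the analysis by any route in the protocol?**

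- PS: no. Section 9.7.3.1 takes its covariates from Table 1, which has no such row.
- Outcome model: no. Section 9.7.3.4 adds PS variables that remain unbalanced, and covariates assessed after the cycle has started, again by reference to Table 1.
- Descriptive or balance tables: no. It is not marked as a baseline characteristic.
- Indirectly through time: no. Calendar year is neither a PS candidate nor a candidate for additional adjustment.
- Indirectly through other PS candidates: in part. Clinic type, age, parity, failed insemination and, in Denmark, the three infertility-cause variables are plausible proxies. None is defined as an indicator of a donor-semen cycle.

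**Step 2. Does Section 9.9.5 answer the point?** It makes two statements: the eligibility rules changed, and changes in standard of care should matter little. The second concerns how women are treated, the first concerns which women are treated. The eligibility change is disclosed but not answered.

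**Step 3. Scale.** The protocol gives no figure on this point, so there is none to reproduce. For one omitted binary covariate, the bias in the risk difference is approximately

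bias = (difference between cohorts in donor-semen share) x (difference in live birth rate between donor-semen and other cycles).

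Both inputs are assumptions: 0 to 10 points for the share and 2 to 10 points for the outcome. Bias in percentage points, before any removal by the proxies:

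| Share difference | Outcome difference 2 | Outcome difference 5 | Outcome difference 10 |
|---|---|---|---|
| 0 | 0 | 0 | 0 |
| 2 | 0.04 | 0.10 | 0.20 |
| 5 | 0.10 | 0.25 | 0.50 |
| 10 | 0.20 | 0.50 | 1.0 |

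For example, 0.05 x 5 = 0.25 and 0.10 x 10 = 1.0.

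**Step 4. Against the protocol's own yardstick.** Section 9.5 states detectable differences of 1.5 points (HP-hMG, both countries), 2.0 points (biosimilars, Sweden) and 2.5 points (biosimilars, Denmark). The share difference needed to reach each one is the detectable difference divided by the outcome difference:

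- 1.5 points: 1.5/0.10 = 15 points of share, or 1.5/0.05 = 30 points.
- 2.0 points: 20 or 40 points.
- 2.5 points: 25 or 50 points.

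All lie outside the assumed range. At the top of that range, 1.0 point is 1.0/1.5 = 67% of the HP-hMG figure and 1.0/2.5 = 40% of the Danish biosimilar figure. At the bottom it is zero.

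**Step 5. On the odds ratio scale.** At the 50% multiple-cycle live birth rate that Section 9.5 uses, a 1.0-point bias is an odds ratio of (0.51/0.49)/(0.50/0.50) = 1.04, and a 0.25-point bias is 0.5025/0.4975 = 1.01.

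**The case against.** The strongest reply is that neither link needed for confounding is documented. Nowhere does the protocol say that donor semen, or single or same-sex status, predicts live birth, or that product choice depends on it. Section 9.9.3 says the products are equally recommended and used interchangeably, although it allows that the cohorts may differ, for instance in cause of infertility. This stands: both links are assumptions, and zero bias belongs in the range.

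Second, Section 9.9.5 does not place the eligibility change in Denmark, or after 26 March 2014, when the Danish biosimilar comparison starts. A change completed before that date would cause no shift within that comparison. This also stands. The documented path runs through calendar time and mainly concerns biosimilars, and adjusting for calendar year would remove the time-driven part. But calendar year is not adjusted for either.

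Third, a reader might infer from Table 1 that this patient mix goes wholly unadjusted. The protocol does not support that, because several PS candidates are partial proxies. Nor does it say how the DIVF codes cause of infertility for a woman without a male partner, so how much the proxies remove is unknown.

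Fourth, a reader might take Section 9.9.5 as dismissing the eligibility change. It does not: it reports the change and then offers reassurance on a different matter.

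Fifth, since the register also holds origin of oocytes, a reader might want that added too. Section 9.2.1 excludes stimulation for oocyte or embryo donation, and the cohorts consist of women's own stimulation cycles. Oocyte origin should therefore hardly vary, and adjusting for it would achieve little.

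Finally, the analysis plan could add covariates. That is possible, but Table 1 is the protocol's own covariate list and Section 9.7.3.1 points to it for the PS.

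**Conclusion.** The gap is real but modest. The protocol acknowledges a changing eligible population, has for Denmark a pre-treatment variable that bears directly on it, and uses that variable in no role. The existing PS candidates cover the mix only in part, and calendar year is outside the PS.

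The size is unknown. Under the assumed ranges it is 0 to about 1.0 point of live birth before any removal by the proxies, below every detectable difference stated in Section 9.5. No direction can be given. It would be going too far to call semen origin an established confounder here, or to say that it could by itself produce a difference as large as the detectable ones: within the assumed ranges it could not. The case for adding it is that the possible bias, though small, does not fall with sample size and can be checked at almost no cost. Availability is documented for Denmark only.

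**What to change.** - For Denmark, add origin of semen (partner, donor) to Table 1 as a baseline characteristic and as a PS candidate.
- Report its distribution by cohort, and its balance before and after weighting, for each pairwise comparison.
- For Sweden, do the same only if the Q-IVF holds the variable.
- If it is left out, say why in Section 9.9.5, and let that section address the eligibility change as well as standard of care.

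Adding semen origin does not replace a decision on whether calendar year should enter the PS.

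The cost is one more variable in the data request and in the PS model. Precision improves only if the variable turns out to be prognostic. Timing matters: Section 6 plans the Danish extraction for August and September 2021, and a variable missing from the request may be hard to obtain afterwards.
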